The study employs a multi-stage cluster sampling method. In the first stage, one central urban area (tentatively identified as Dongcheng Street, which oversees 31 primary schools) and one non-central urban area (tentatively identified as Gaobu Town, which oversees 13 primary schools) will be randomly selected, reflecting the urban-rural structure of Dongguan City. In the second stage, ten primary schools will be randomly selected from each administrative district, with five designated as intervention group schools and the remaining five as control group schools. This results in a total of twenty primary schools, evenly split between the intervention and

control groups. In the third stage, two classes from each of the two grades (fourth and fifth grades) are randomly selected from each of the twenty selected schools using a cluster sampling method, with surveys conducted at the class level. Each school comprises a minimum of 152 students. Schools with 152 students will have one additional class randomly selected. The final estimated total sample size is projected to be 3036. Random sampling and randomized grouping are achieved using computer software to generate random numbers. The sample size is determined using the following formula:

$$n = \frac{\left\{ z_{1-\alpha/2} \sqrt{2(m-1)\rho + 2} + z_{\beta} \sqrt{m\rho + 1} \right\}^2 * \{p_1(1-p_1) + p_2(1-p_2)\}}{(p_1 - p_2)^2}$$

where: n is the desired sample size for each cohort, $z_{1-\alpha/2}$ is the value corresponding to the accepted Type I error rate (eg $z_{1-\alpha/2}$ about 1.96 for an error rate of 0.05), z_{β} is the value corresponding to the desired statistical power, e.g., for a power of 0.8, z_{β} is approximately 0.84. m is the size of each cohort, ρ is the intra-group correlation coefficient, p_1 is the expected outcome rate in the test group (ie, influenza vaccination rate), and p_2 is the expected outcome rate in the control group. Based on the assumption that the anticipated influenza vaccination rate is 80% in the intervention group and 50% in the control group, the estimated sample size, denoted as 'n', is 138 students per school.^{13, 14} This implies that approximately 138 primary school students are required for each group, yielding a total sample size of 2760 individuals. To account for potential sample attrition, the sample size is expanded by 10%, resulting in a final estimated total sample size of 3036 for statistical analysis.

Intervention methods

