Staff of the affiliated street Center for Disease Prevention and Control (CDC) will visit the school in the first month to implement intervention activities using the health education intervention package. The intervention period will commence in September 2023 and conclude in February 2024, resulting in a total intervention duration of approximately three to four months. The specific intervention process is as follows: 1) At the start of the semester (early intervention stage in September 2023), initiation activities will be conducted. The investigators will introduce the study to teachers and students, and medical professionals or public health experts will be invited to deliver classroom lectures at the intervention group schools. Baseline data will be collected at this stage. 2) During the intervention period (September 2023 – January 2024), the intervention group will follow the health education intervention toolkit to conduct intervention activities. 3) At the conclusion of the semester (February 2024), follow-up data will be collected. The intervention timeline is shown in the Figure 2.

Data collection and analysis

Questionnaire surveys will be administered to students and parents before and after

the intervention, using self-completion. The questionnaire design, which is informed by similar research literature (Appendix 1 & 2), will undergo evaluations for reliability and validity. The questionnaire will include the following content: 1) Socio-demographic characteristics (name, age, sex, class, residential address, parents' educational level, occupation, family income); 2) Personal history (basic disease history, allergy history, and personal history); 3) Influenza vaccination health literacy level. The health literacy level concerning influenza vaccination will be assessed across four dimensions: knowledge, attitude, behavior, and skills related to influenza vaccination. Details of these four dimensions include knowledge of basic facts about the influenza vaccine (such as its efficacy, vaccination frequency, and side effects), attitudes towards the influenza vaccine (including perceptions of its efficacy and safety), behavioral characteristics related to influenza vaccination (such as willingness to be vaccinated, vaccination status, and timing of vaccination), and sources of information about the influenza vaccine.

Confirmation of influenza and surveillance of influenza-like cases

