Primary outcomes include the influenza vaccination rate and the influenza vaccination health literacy level. The influenza vaccination rate will be calculated as the number of vaccinated individuals divided by the total number of individuals, multiplied by 100%. Regarding the influenza vaccination health literacy level, each correct answer for the scale will be scored as one point, with incorrect answers receiving no points. Based on the scores, health literacy levels will be categorized as low, medium, or

high.

Secondary outcomes include influenza incidence, the ILI incidence and the influenza vaccine protection rate. The influenza incidence will be calculated as the number of individuals diagnosed with influenza divided by the total number of individuals, multiplied by 100%, The ILI incidence will be calculated as the number of ILI cases divided by the total number of participants, multiplied by 100%. The influenza vaccine protection rate will be calculated as the difference between the incidence rate in unvaccinated individuals and the incidence rate in vaccinated individuals, divided by the incidence rate in unvaccinated individuals, multiplied by 100%.

Statistical analysis plan

Continuous variables will be described using means \pm standard deviation or median (interquartile range), and comparisons will be made using two independent samples t-tests or Wilcoxon rank-sum tests. Categorical variables will be described using frequency and composition ratios, and rate comparisons will be conducted using Chi-square tests or Fisher's exact probability method. The association between the level of influenza vaccination health literacy and vaccination willingness will be analyzed using multivariate logistic regression.

Quality control

Quality Control will be conducted in accordance with the requisite quality control standards, with dedicated on-site quality control personnel assigned to oversee investigation and evaluation. These personnel should be proficient in various testing technical requirements and quality control points, and familiar with the on-site

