Have you heard of the influenza or flu?

Do you know what the symptoms of having the flu are?

Do you think you can spread the flu to other people when you get it?

Do you think you can go to class after getting the flu?

Have you heard of the flu vaccine?

Do you know what the flu vaccine does?

Do you know how the flu vaccine works? (For example, it helps our body learn how to beat the flu virus)

Attitude Questions

Do you think getting a flu vaccine is a good thing or a bad thing?

Are you afraid of getting the flu vaccine? Why?

Behavioral questions

Within the last year, have you had the flu (or had flu-like symptoms such as sudden high fever, temperature over 38°C, general lack of energy, headache, sore throat, etc.)?

If yes, when was the last time you had influenza (or had a sudden onset of illness with high fever $\geq 38^{\circ}\text{C}$ accompanied by influenza-like symptoms such as generalised malaise, myalgia, sore throat, etc.)?

Have you been vaccinated against flu in 2023?

If you have been vaccinated, when did you get your flu vaccine in 2023?

Would you like your parents to take you for a flu vaccination?

Skill Questions

Where do you get information about flu vaccinations?

Who do you ask if you have questions about the flu vaccine?

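### The literacy primary outcome is defined to include vaccination status and timing, so if those items score, extra vaccinations raise literacy without any change in knowledge, attitude or skills

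*Combined protocol and SAP*

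**What the plan says.** Study outcomes in the combined protocol and SAP states: "Primary outcomes include the influenza vaccination rate and the influenza vaccination health literacy level". Data collection and analysis builds the literacy level from knowledge, attitude, behavior and skills, and describes the third as "behavioral characteristics related to influenza vaccination (such as willingness to be vaccinated, vaccination status, and timing of vaccination".

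The questionnaires match. In Appendix II (student form), the behavioral block asks "Have you been vaccinated against flu in 2023", followed by a date question that only a vaccinated child can answer. Appendix I (parent form) has equivalent items about the child.

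Study outcomes gives one point per correct answer and none for an incorrect one, then groups scores as low, medium or high. It gives no item key and no cut-offs, excludes no items, and does not say whether the student or the parent form is scored.

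Under Intervention methods, the intervention package contains a self-paid vaccination service and a medal for vaccinated students. The control arm has routine health education only.

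**The concern.** Objective 2 compares the arms on vaccination rate and on literacy as two parameters. As defined, one sits inside the other. The service and the medal can raise uptake through access and incentive. If the vaccination items score, that uptake passes straight into the literacy score.

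The trial could then report that health education improved literacy when answers on knowledge, attitude and skills had not moved. A second positive primary outcome would look like separate evidence and would not be. The Statistical analysis plan names no analysis by dimension that would show this.

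**Working it through.** **The plan's own figure.** The sample size rests on vaccination rate only: "influenza vaccination rate is 80% in the intervention group and 50% in the control group", z "about 1.96 for an error rate of 0.05", and "for a power of 0.8" a z of 0.84. The formula's m and ρ are defined ("m is the size of each cohort"; ρ "is the intra-group correlation coefficient") but given no values, so 138 can be neither confirmed nor refuted. With m = 138 it is recovered at ρ = 0.0096:

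- (1.96√(2×137×0.0096 + 2) + 0.84√(138×0.0096 + 1))² × 0.41/0.09 ≈ 138, where 0.41 = 0.8×0.2 + 0.5×0.5.
- 138 × 20 = 2760, and 2760 × 1.10 = 3036.

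No figure is given for literacy.

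**Item counts (mine, from the appendices).** Student form: 7 knowledge + 2 attitude + 5 behavior + 2 skill = 16. Parent form: 10 + 15 + 14 + 3 = 42.

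**Shift from uptake alone.** Let all other answers be distributed alike in both arms.

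- Status item scored: (0.80 − 0.50) × 1 = 0.3 points.
- Status and date scored: (0.80 − 0.50) × 2 = 0.6 points.

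**Chance of a significant literacy result.** From the plan: 10 schools per arm, 138 students per school (1380 per arm), two-sided 5%. Assumed, because the documents give neither: student-form score SD 2.5-3 and literacy ICC 0.01-0.05. The test compares school means (noncentral t, 18 df):

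SE = SD × √(2[1 + 137 × ICC]/1380)

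Example, SD 2.5 and ICC 0.01: SE = 2.5 × √(2 × 2.37/1380) = 0.1465. For 0.3 points the noncentrality is 0.3/0.1465 = 2.05 and the rejection rate is 49%.

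| SD | ICC | SE | 0.3 points | 0.6 points |
|---|---|---|---|---|
| 2.5 | 0.01 | 0.147 | 49% | 97% |
| 2.5 | 0.02 | 0.184 | 34% | 87% |
| 2.5 | 0.05 | 0.267 | 19% | 57% |
| 3 | 0.01 | 0.176 | 37% | 90% |
| 3 | 0.02 | 0.221 | 25% | 73% |
| 3 | 0.05 | 0.320 | 14% | 43% |

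With the items removed the expected difference is 0 and the rate is the nominal 5%. A simulation of the 16-item form (600 runs per scenario, SD about 3) agrees. At ICC 0.01 and 0.05 the school-level test rejected in 34% and 18% of trials with one item, 89% and 42% with two, and 5-6% with none.

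**Sensitivity.**

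- *Smaller uptake gap.* A 10-point gap gives 0.1 points for one item, and the rate falls to 6-10% over the same SD and ICC range. Two items (0.2 points) give 9-25%.
- *Parent form.* With 42 items and a simulated SD near 7, the school-level test at ICC 0.01-0.05 rejected in 8-9% of simulated trials with one item and 15-30% with two, at 80% v 50%.
- *Three-level outcome.* With assumed cut-offs at 60% and 80% of the score and ICC 0, a Chi-square test rejected in 53% (one item) and about 100% (two items) on the student form, and in 11% and 42% on the parent form.

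**The case against.** The best defence is that a point goes only to a correct answer, and a question about whether or when a child was vaccinated has no obvious correct answer. The items may be meant for collection and not for scoring, and then the numerical effect vanishes. This stands as a limit: a reader might infer that contamination of the score is established, and the documents do not show that. They show a definition that includes the items and a scoring rule that does not remove them. If the items score nothing, the four-dimension definition is not what Study outcomes scores, and the text still needs correcting. The date item has the weaker claim to a point, so the 0.6-point column rests on the weaker assumption.

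It is also fair that 80% v 50% is the expected effect of the whole package, teaching included, and that the service is voluntary and self-paid. Assigning the full gap to access and incentive with no learning is the extreme case, and the sensitivity figures show how fast the effect shrinks.

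A reader might prefer the rejection rate of the planned student-level t-test, which is higher: 64-78% for 0.3 points at ICC 0.01-0.05. That does not measure this problem. At those ICCs the same test rejects in 20-48% of trials with no vaccination item scored, because it ignores clustering, which is a separate fault.

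Last, the Introduction treats behavior as part of vaccination literacy, so a behavior dimension is a declared choice. That justifies keeping a behavior dimension. It does not justify counting the other primary outcome inside it.

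**Conclusion.** The point holds conditionally. It is certain from the text that the second primary outcome is defined to contain the first and that nothing takes the shared items out. Whether this biases the literacy comparison depends on those items earning points.

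If they do, and at the planned uptake on the student form, a correct school-level test finds a literacy difference without any change in knowledge, attitude or skills in 14-49% of trials (one item) or 43-97% (two items), against 5%. These figures rest on assumed SD 2.5-3 and ICC 0.01-0.05. The effect is modest on the parent form, and near nominal with a 10-point gap and one item. A spurious result is possible, not assured.

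A reader might also infer that willingness, or the whole behavior dimension, must leave the score. The overlap does not require that: willingness is not the first primary outcome.

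**What to change.** In Data collection and analysis and in Study outcomes, state before follow-up data are examined that:

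- vaccination status, vaccination date and illness-history items, with their follow-on questions, are not scored in the primary literacy level;
- vaccination status counts only in the vaccination-rate outcome, and the unscored items are reported separately;
- a named form (student or parent) supplies the primary score, with a key showing which answer to each scored item is correct.

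Willingness may stay. On the parent form, one willingness question is put only to parents of unvaccinated children, so the key should say how it is handled.

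The cost is wording and no new data. The scale is shorter: on the student form two vaccination and two illness-history items go, leaving 16 − 4 = 12, with willingness the only behavior item.

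### The primary literacy score counts correct answers, but on the student form at least 10 of the 16 printed items have no correct answer

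*Combined protocol and SAP*

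**What the plan says.** The Study outcomes section states: "Primary outcomes include the influenza vaccination rate and the influenza vaccination health literacy level". For literacy, "each correct answer for the scale will be scored as one point, with incorrect answers receiving no points", and the total is then grouped into three levels. No cut-points are given.

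Data collection and analysis says the level will be "assessed across four dimensions: knowledge, attitude, behavior, and skills related to influenza vaccination". It describes the behavior dimension with examples, "such as willingness to be vaccinated, vaccination status, and timing of vaccination", and ends the list of dimensions with sources of information. Students and parents complete the forms themselves, before and after the intervention. The questionnaire is to be evaluated for reliability and validity, without further detail.

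Appendix I (parent form) and Appendix II (student form) print question stems without response options. The student form includes "Have you heard of the flu vaccine" under knowledge, "Are you afraid of getting the flu vaccine? Why" under attitude and "Where do you get information about flu vaccinations" under skill. The plan gives no answer key and no list of scored items, and does not say which form supplies the primary score.

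**The concern.** A right/wrong rule needs items with a right answer. Willingness, vaccination date, fear and information source have none, so the stated rule cannot be applied to the scale as the plan describes it. Someone will have to decide later which answers earn a point, and nothing prevents that decision being made after data are seen.

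There is also a possible bias between arms. Only intervention schools receive the study's lectures, booklets and videos on influenza vaccine. The forms are self-completed, and the SPIRIT checklist marks blinding as not applicable. A child who attended a lecture has heard of the vaccine whether or not a fact was learned. If that answer earns the same point as a demonstrated fact, the score mixes familiarity with literacy. Separately, if the vaccination-status item were scored, the literacy outcome would contain part of the other primary outcome.

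**Working it through.** The plan states no figure to reproduce, so the check is a count of the printed stems in the four literacy sections of each form.

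**Student form (Appendix II)**

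| Section | Item type | Items | Can be marked right or wrong? |
|---|---|---|---|
| Knowledge | Factual (spreading flu; attending class) | 2 | Yes, as worded |
| Knowledge | 'Do you know' | 3 | Only if unprinted options test facts |
| Knowledge | 'Have you heard' | 2 | No |
| Attitude | Vaccination good or bad | 1 | Only if the opinion is keyed |
| Attitude | Fear, with reason | 1 | No |
| Behaviour | Illness history (2), vaccination status and date (2), willingness (1) | 5 | No |
| Skill | Information source; whom to ask | 2 | No |

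Total: 7 + 2 + 5 + 2 = 16.

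- Strict coding: 2 of 16 can be scored; 14 of 16 (88%) cannot.
- Most generous coding: 2 + 3 + 1 = 6 of 16 can be scored. The remainder is 2 + 1 + 5 + 2 = 10 of 16 (63%).

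**Parent form (Appendix I)**

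There are 10 knowledge + 15 attitude + 14 behaviour + 3 skill = 42 stems.

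- Factual as worded: 2 knowledge + 10 attitude = 12. Without a correct answer: 30 of 42 (71%).
- Keying the 5 opinion items as well: 17. Without: 25 of 42 (60%).
- Also treating all 8 'Do you know' stems (7 knowledge, 1 skill) as factual: 25. Without: 17 of 42 (40%), made up of 14 behaviour, 1 'Have you heard' and 2 on interest or information source.

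**Both forms together**

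Of 58 stems, 30 + 14 = 44 (76%) have no correct answer under strict coding, and 17 + 10 = 27 (47%) under the most generous.

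**How much could come from exposure**

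Of the 7 student knowledge points, 2 (29%) are for having heard of something. If the three 'Do you know' items are answered yes or no, 5 of 7 (71%) can be earned without a correct fact. That format is an assumption. One of the three, on how the vaccine works, prints a hint in brackets and reads most naturally as yes/no; the format of the others cannot be inferred.

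As an illustration, suppose lectures raise 'yes' answers by 10 to 20 percentage points on the affected items and change nothing else (assumed; not in the documents). The difference between arms is the number of items times the shift:

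- 'Have you heard' items only: 2 × 0.10 = 0.2 to 2 × 0.20 = 0.4 point.
- All five items, if yes/no: 5 × 0.10 = 0.5 to 5 × 0.20 = 1.0 point out of 7.

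**The case against.** The strongest reply is that the appendices print stems only. A rule about correct answers fits multiple-choice options at least as well as yes/no, and several parent stems (flu season, transmission, minimum age for vaccination) have natural factual options. This stands: the 'Do you know' items cannot be called self-rated as a fact, and the 71% is conditional. But options can rescue only those items; they cannot make having heard of something, fear, illness history or vaccination date right or wrong.

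Second, the plan never says that every item is scored, so scoring only the items that have an answer would be consistent with it. That is fair, but the plan defines the level across all four dimensions and names no subset.

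Third, information sources belong to the construct, since the Introduction's definition of health literacy includes acquiring information, and sources could be ranked by reliability. Such a ranking would be a new scoring rule, and the plan gives none. Reporting these items separately keeps them in the study.

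Fourth, the baseline survey introduces influenza vaccine to control children too, which should narrow the gap on the two 'Have you heard' items. This stands and limits the likely bias. The planned reliability and validity evaluation also counts for something, but it neither supplies a key nor says which items score.

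A reader might go further and infer that most items on both forms are unscorable. The documents do not support that: under generous coding the parent form falls to 40% and the two forms together to 47%. 'Most' holds under every coding above only for the student form.

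**Conclusion.** The concern holds. The stated rule does not fit the scale it is applied to. On the student form 2 of 16 items can be scored as worded and at most 6 under the most favourable reading, leaving 10 to 14 without a correct answer. The upper limit of 6 assumes factual options for all three 'Do you know' items, a key for the opinion item, and no reliability ranking of information sources. The parent form is affected less (17 to 30 of 42), because many of its attitude items can be keyed.

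A higher score in the intervention arm could therefore partly reflect familiarity. A reader might infer that the trial could not conclude anything about literacy. That is too strong: the lectures are meant to raise knowledge, some items do test facts, and the documents give no measure of how large an exposure effect would be. The supported conclusion is that, as specified, the score cannot separate familiarity from learned facts.

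**What to change.** Rewrite the scoring paragraph under Study outcomes as follows.

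- Name the form that supplies the primary score. List the items scored right or wrong, each with its keyed answer. Fix the list and key before baseline, or at the latest before follow-up data are seen.
- Give the 'Do you know' items answer options with a keyed response, on both forms, or leave them out of the score. If baseline forms are already in use, leaving them out avoids changing the instrument between surveys.
- Take 'Have you heard', behaviour (vaccination status, timing, willingness, illness history), fear and information-source items out of the score and report them separately.
- Score attitude items as a separate subscale with a stated direction.
- Set the cut-points for the low, medium and high levels on the revised score at the same time.

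The work is one scoring paragraph and, if done before baseline, response options for a few items. The cost is a shorter scored scale, especially for students, and literacy reported by subscale and not as one total. If the 'Do you know' and opinion items are left out, only 2 student items remain in the right/wrong score, which is a strong reason to add keyed options before baseline if that is still possible.

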The proposed study is a cluster randomized controlled trial. Two administrative districts, one in the central urban area and the other in the non-central urban area of Dongguan, will be selected for this study. Within each district, ten primary schools will be randomly selected, with half designated as intervention group schools and the remaining half as control group schools. This results in a total of twenty primary schools, evenly split between the intervention and control groups.

The intervention group will receive a health education intervention focused on influenza vaccination, while the control group will continue with their routine school health education. The intervention period for this study is projected to last approximately three to four months. Data collection will conduct at the onset and conclusion of the intervention period. The primary outcomes of interest are the differences in influenza vaccination rates and influenza vaccination health literacy levels between the experimental and control groups, which will be used to evaluate

the effectiveness of the intervention. The overview of the study procedure is shown in the Figure 1.

Study sample

Study participants are primary school students in grades 4 to 5 in Dongguan City.

Inclusion criteria include: 1) Primary school students within the age range of 7-12 years. 2) Students and their parents who voluntarily agree to participate in the study and provide signed informed consent. 3) Permanent residents of Dongguan City who are expected to complete the project without transferring schools during the study period.

In addition, individuals with contraindications to influenza vaccination, who have recently received an influenza vaccination, diagnosed with influenza or confirmed as influenza-like cases at the commencement of the study, or unwilling to participate in the project, will be excluded.

Sampling method

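### The primary literacy outcome is a score cut into three levels with no stated cut-points and no named test; the score itself should be primary, with scoring and cuts fixed in advance.

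*Combined protocol and SAP*

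**What the plan says.** Study outcomes: "Primary outcomes include the influenza vaccination rate and the influenza vaccination health literacy level". On scoring, "each correct answer for the scale will be scored as one point, with incorrect answers receiving no points"; then "Based on the scores, health literacy levels will be categorized as low, medium, or" high. Study design describes the arm comparison as "the differences in influenza vaccination rates and influenza vaccination health literacy levels between the experimental and control groups".

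No cut-point, cut rule, maximum score or scoring key appears in Study outcomes, in Data collection and analysis, or in the parent and student questionnaires (Appendices I and II).

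The Statistical analysis plan section gives rules by type of variable only. For continuous variables, "comparisons will be made using two independent samples t-tests or Wilcoxon rank-sum tests"; for categorical variables, "rate comparisons will be conducted using Chi-square tests or Fisher's exact probability method". Neither rule is tied to literacy. The only analysis that mentions literacy is a logistic regression relating its level to willingness to be vaccinated, which is not a comparison of arms.

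**The concern.** The trial will hold a point score for each respondent, but the named outcome is a three-way grouping of it. If that grouping is tested under the categorical rule, two things follow.

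- **Lost information.** A chi-square or Fisher test treats low, medium and high as unordered, so a move from low to high is simply a different cell from a move from low to medium. A gain that stays inside a level counts for nothing.
- **Open cut-points.** With no cuts written down, they could be set once the scores are known, and the significance of a primary outcome can turn on that choice.

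The second matters more. It bears on the false-positive rate and does not depend on how much power the grouping costs.

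**Working it through.** **No figure to reproduce.** The sample size (138 x 20 = 2,760; 2,760 x 1.10 = 3,036) rests on vaccination rates of 80% and 50%. No SD, effect size, ICC or power is given for literacy, so everything below is illustrative.

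**Inputs.** From the plan: two-sided 5% and 80% power (both given as examples in Sampling method), 10 schools per arm, 138 students per school. Assumed: an approximately normal score with SD 1, and ICC 0.01 to 0.05.

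**1. Independent students.** A score test with 80% power has noncentrality (1.960 + 0.842)² = 7.85. Cutting the score into levels with proportions p_j keeps the fraction E = Σ (φ_lower − φ_upper)² / p_j, where φ is the normal density at each cut (0 at the ends).

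- Tertiles: cuts at ±0.431, φ = 0.3636. E = 2 x 0.3636² / (1/3) = 0.793. Noncentrality 7.85 x 0.793 = 6.23.
- 5/15/80: cuts at −1.645 and −0.842, φ = 0.1031 and 0.2800. E = 0.1031²/0.05 + (0.2800 − 0.1031)²/0.15 + 0.2800²/0.80 = 0.213 + 0.208 + 0.098 = 0.519. Noncentrality 4.07.

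Power from the noncentral chi-square distribution:

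| Split | E | Unordered, 2 df | Ordered, 1 df |
|---|---|---|---|
| Tertiles | 0.79 | 60% | 70% |
| 10/30/60 | 0.70 | 55% | 65% |
| 5/15/80 | 0.52 | 42% | 52% |

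**2. School-level analysis, 10 v 10 schools.** The variance of a school mean score is V = ρ + (1 − ρ)/138. A t-test on 18 df needs noncentrality 2.963 for 80% power. A grouped version whose squared correlation with the score is r² has variance V_g = r²ρ + (1 − r²ρ)/138 and noncentrality 2.963 x r x √(V/V_g). With tertile cuts, r² = 0.793 for the mean level (levels equally spaced) and 0.3636² / (1/3 x 2/3) = 0.595 for the percentage high.

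| ICC | V | V_g, mean level | Noncentrality, power | V_g, % high | Noncentrality, power |
|---|---|---|---|---|---|
| 0.01 | 0.01717 | 0.01512 | 2.81, 76% | 0.01315 | 2.61, 70% |
| 0.05 | 0.05688 | 0.04662 | 2.92, 79% | 0.03678 | 2.84, 77% |

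Simulation of this design gave 79%, 76% and 68% (score, mean level, percentage high) at ICC 0.01, and 80%, 78% and 76% at ICC 0.05. A repeat gave 80%, 76% and 70%, and 80%, 79% and 78%. Across these the loss is about 1 to 4 points for the mean level and about 2 to 11 for the percentage high. With the high level cut at the 95th percentile, simulated power for the percentage high falls to 46% (ICC 0.01) and 65% (ICC 0.05).

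**3. Choice of cuts.** Seven plausible pairs of cuts were applied to the same simulated data (assumed 16-item score, 500 independent students per arm). With a real effect the score had 79% power and the chi-square 49% to 61%. Significance depended on which pair was used in 52% of trials. With no effect each pair held about 5%, but at least one pair was significant in 16%.

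**The case against.** The strongest reply is that the plan nowhere says the level will be tested by chi-square. It defines a point score and lists tests for continuous variables, it words the categorical rule as one for rates, and Data collection and analysis uses the word level for the construct as a whole. This stands in part: the categorical test is an inference. But the outcome is named as a level and compared between arms as levels, and the score is never named as an endpoint. The silence leaves both score-versus-level and the cuts open.

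A reader might also infer that the trial's power on literacy drops to 60% or 42%. The documents do not support that. Those figures need independent students and an unordered test, whereas schools are randomized. Once schools are allowed for, between-school variation dominates and the loss is small unless the cuts are extreme.

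Nor do the documents show that a real gain would be missed. With 1,380 independent students per arm, the effect that the score detects with 80% power is 2.80 x √(2/1,380) = 0.107 SD; at 0.2 SD the three-level chi-square would have 99% power at tertiles and 93% at 5/15/80. Nothing in the plan points to a 5/15/80 split. If a short scale reached its ceiling, the score would itself carry less information: on assumed 7- to 16-item scales with roughly 80% of children in the top level, chi-square power was about 47% to 60%, not 42%.

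Finally, moving to the score is not enough while the score is undefined. The student and parent forms differ, several items have no correct answer, and the behavior dimension includes vaccination status. This is right, and the fix covers it.

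**Conclusion.** The point holds in a limited form. A primary outcome is defined by cuts that are not written down, and no test is named for it; the plain reading is a categorical test that ignores order and within-level gains.

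The loss of power runs from about 20 points (80% to 60%) at tertiles to 38 points (80% to 42%) at 5/15/80 for an unordered test on independent students. It is about 1 to 4 points (mean level) or 2 to 11 points (percentage high) in a school-level analysis with tertile cuts. All of this assumes a roughly normal score and ICC 0.01 to 0.05, and none of it is a forecast for this trial. The firmer ground is the open choice of cuts: at least one of seven pairs was significant in 16% of simulated trials with no effect. That shows what the wording permits; nothing in the documents suggests an intention to choose cuts after seeing the scores.

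The change should be made because the score is already to be collected and the better analysis costs little.

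**What to change.** In Study outcomes and Statistical analysis plan:

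1. Make the student total score at the February 2024 follow-up the primary literacy measure. List the scored items with a key, counting only items that have a correct answer and excluding vaccination status, which is the other primary outcome.
2. Estimate the difference in mean score between arms, in points, adjusted for baseline score and district, by a mixed model or a school-level analysis. Using the score does not by itself deal with clustering: individual-level tests that ignored school had simulated type I error of 14% (chi-square) and 20% (t-test) at ICC 0.01, and 39% and 48% at ICC 0.05.
3. Keep low, medium and high as a descriptive display, with cut-points fixed before follow-up scores are examined. If the level is tested, use an ordered test that allows for schools.

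The cost is plan wording and a scoring key; no new data or visits are needed, since the baseline questionnaire is already planned. The small downside is that a mean difference in points is less immediate for a lay audience than a percentage high, which can still be shown alongside it.
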